5.4. Safety Endpoints

- Potential adverse consequences: Change in mental (CESD) or physical health (heart rate, blood pressure, weight).
- Increased TNE (corrected by creatinine), calculated as change from Phase 1 baseline.
- Adverse events and Serious Adverse events.

6. Statistical Analysis

6.1. General Approach

All statistical analyses will be performed using SAS or R. All statistical tests will be two-tailed. A Bonferroni multiple-comparisons adjustment will be used to account for multiple comparisons for each of the two primary endpoints ($\alpha = 0.025$). Analyses of the secondary and exploratory endpoints will not be adjusted for multiple comparisons ($\alpha = 0.05$). All analyses will be completed using the intent-to-treat principle unless otherwise noted. Methods for handling missing data will be specified below.

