3.1. Randomization

Subjects will be randomized at the end of Phase 2 with a 1:1 ratio to the two studied conditions described above. Randomization will be stratified by site using a blocked randomization scheme with random block sizes of 2, 4, and 6. We anticipate no or less than minimal block effects in our data based on previous studies with similar design.

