3.2. Sample Size

Sample size was re-estimated for this project by [name] on 8/21/2019. After discussion with members of the CENIC External Advisory Board and representatives of the National Institute of Drug Abuse and Food and Drug Administration, we changed the sample size from 700 to 500.

More power analysis was performed on 11/10/2021 for 2 smaller sample sizes (N = 450 and 400), with all the other parameters being the same as the power analysis performed on 8/21/2019.

We will enroll at least 400 rather than the 700 subjects originally proposed (200 per group) to the study and assume a 20% attrition rate over the 12-week post randomization period. Power analysis was performed for two of the primary outcomes in the primary aim: CPD smoked at the end of Phase 3 and smoke-free days during Phase 3.

3.2.1 Methods: See Section 6.9 for interim analysis and the methods for the sample size re-estimation.

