3.2.3 Power re-estimation

The power re-estimation is based on a total of 500, 450, and 400 enrolled subjects with a 20% attrition rate over the 12-week post randomization period. Power analysis was performed for the two primary outcomes: CPD smoked at the end of Phase 3 and smoke-free days during Phase 3. The effect of the two primary outcomes was assumed to be the same as previously assumed: 7 and 15 mean CPD for the VLNC and NNC group; and a 11 day difference (we assumed 12 abstinence days vs. 1 abstinence day, out of 84 days, previously) in the smoke-free days for VLNC vs. NNC. The nuisance parameters were based on the interim analysis (see Section 6.9 and Table 1 above).

The two-sided type-I error rate for each outcome (CPD and abstinence) was set at $\alpha=0.025$ ($=0.05/2$ outcomes by the Bonferroni method) for the overall sample as previously designed. The type I error rate for the gender subgroup analysis was set to be α divided by the number of subgroups ($=2$) as previously designed. The type I error rate for the age subgroup analysis was set to be α divided by 2, rather than 3 because based on the interim data, there were <1% of participants in the 18-24 age group, hence, this age group was dropped from the power analysis. The Subgroup Analysis section (Section 6.6) in the SAP was revised accordingly.

The same statistical methods were used as previously designed. Specifically, t-test was used for the CPD outcome. For the smoke-free days outcome, we first calculated the rate of smoke-free days by dividing the number of smoke-free days by the total number of days in Phase 3 (84 days) and then used z-test for the Poisson rate difference. PASS 14 was used for power calculations.

The estimated power for 500, 450, and 400 subjects is presented in Table 2.

Table 2. Power Analysis for Total Enrolled N=500, 450, and 400

Primary outcomes	VLNC	NNC	Overall sample	³ Subgroup analysis by sex		⁴ Subgroup analysis by age		
				F	M	18-24	25-44	45+

N enrolled = 500								
¹ Cigarettes (study or non-study) per day smoked at the end of Phase 3 (calculated as mean CPD based on 7 days' IVR data before the week 12 visit)	7	15	>.99	>.99	>.99	-	>.99	>.99
² Number of smoke-free days during Phase 3 (12 weeks or 84 days)	11 days difference		.94	.55	.61	-	.72	.41
N enrolled = 450								

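### Each primary endpoint is tested at a fixed 0.025; Holm's procedure would keep the same family-wise 0.05 and add a few points of power for smoke-free days

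*Combined protocol and SAP*

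**What the plan says.** SAP 6.1 and protocol 16.6.1 carry the same rule: "A Bonferroni multiple-comparisons adjustment will be used to account for multiple comparisons for each of the two primary endpoints", with alpha of 0.025 for each. They add that "All statistical tests will be two-tailed". SAP 3.2.3 and protocol 16.3 use the same split, 0.05 divided by two outcomes, in the power calculation. Neither document contains a step-down, hierarchical or alpha-recycling rule.

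The power calculation takes "7 and 15 mean CPD for the VLNC and NNC group; and a 11 day difference" as the effects and says to "assume a 20% attrition rate over the 12-week post randomization period". For smoke-free days the authors divided days by 84 and "then used z-test for the Poisson rate difference". SAP Table 2 gives overall CPD power above .99 at N = 500, 450 and 400, and smoke-free-days power of .94, .92 and .88.

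SAP 6.6 and protocol 16.6.6 set the sex and age subgroup tests at half of the alpha pre-specified for the outcome in the overall sample, which is 0.0125 for a primary endpoint.

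**The concern.** The two primary endpoints are very unequally powered. CPD is close to certain to pass 0.025 on the plan's assumptions, while smoke-free days is the weaker endpoint and the sample was cut from 700 to 500 and then to 400-450. Under plain Bonferroni, the 0.025 spent on CPD cannot be reused once CPD has been rejected. Holm compares the smaller p-value with 0.025 and, if that rejects, the other with 0.05. It needs no assumption about how the endpoints are correlated. At stake is some power on smoke-free days, available without more participants.

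**Working it through.** **Inputs.** SAP Table 1: pooled CPD SD 9.62; NNC smoke-free rate r0 = 0.0504. SAP 3.2.3: CPD difference 15 − 7 = 8; smoke-free difference 11/84 = 0.13095, so the VLNC rate is r1 = 0.0504 + 0.13095 = 0.18135. Allocation is 1:1 (SAP 3.1). With 20% attrition, n = 160, 180 and 200 per arm for N = 400, 450 and 500.

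**Step 1: reproduce the stated power, smoke-free days.** Power = Φ[(r1 − r0)/√((r0 + r1)/n) − z], where z = 2.2414 at two-sided 0.025 and 1.9600 at 0.05, and r0 + r1 = 0.23175.

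For n = 160, the SE is √(0.23175/160) = 0.03806 and the ratio is 0.13095/0.03806 = 3.441. At 0.025 this gives Φ(3.441 − 2.241) = .885.

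| N | Stated, 0.025 | Reproduced, 0.025 | At 0.05 | Gain (points) |
|---|---|---|---|---|
| 400 | .88 | .885 | .931 | 4.6 |
| 450 | .92 | .920 | .954 | 3.4 |
| 500 | .94 | .946 | .970 | 2.5 |

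The stated values reproduce to within a point.

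**Step 2: how often Holm would open the 0.05 level.** For CPD at N = 400, SE = 9.62 × √(2/160) = 1.0755. The assumed difference gives 8/1.0755 = 7.44, so the probability of p ≤ 0.025 exceeds .9999. Probabilities at smaller true differences, from the noncentral t at N = 400:

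| CPD difference | P(CPD p ≤ 0.025) |
|---|---|
| 5 | .99 |
| 4 | .93 |
| 3 | .70 |
| 2 | .35 |

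Simulating both statistics at N = 400 with correlation 0.5, Holm's smoke-free-days power was .932 at a difference of 8, .923 at 4, .905 at 3 and .890 at 2, against about .885 for Bonferroni throughout.

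**Step 3: error rates.** Under the global null, the simulated family-wise error was identical for the two methods: 0.049, 0.046 and 0.040 at correlations 0, 0.5 and 0.8. With CPD truly different and smoke-free days null, the smoke-free-days error was 0.025 under Bonferroni and 0.050 under Holm.

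**Step 4: sensitivity to the variance.** The Poisson z-test gives each participant's smoke-free proportion a variance equal to its mean. A proportion between 0 and 1 cannot have variance above r(1 − r). The cap is therefore 0.0504 × 0.9496 + 0.18135 × 0.81865 = 0.1963, against 0.2318. On the same rate-difference scale:

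| N | At 0.025 | At 0.05 | Gain (points) |
|---|---|---|---|
| 400 | .933 | .962 | 2.9 |
| 450 | .958 | .977 | 2.0 |

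At 75% of the cap (an assumption), the gain is about 1 point or less.

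The planned regression works on a log-rate scale. A rough approximation there uses log(r1/r0) = 1.280 and variance [(1 − r0)/r0 + (1 − r1)/r1]/n. It gives gains of about 5 points (N = 400) and 4 points (N = 450) at the cap, and 2.4 and 1.5 points at 75% of it.

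**The case against.** The strongest reply is that nothing here is wrong. Bonferroni is valid, pre-specified and applied consistently in the power and analysis sections, and the plan's own power for smoke-free days is .88 at the minimum N. That stands: a reader might infer that the plan has made an error or leaves this endpoint underpowered, and the documents support neither.

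A reader might also infer that Holm costs nothing in error rate. Family-wise error does stay at or below 0.05. But in the very case where Holm helps, with CPD truly different, the chance of a false claim on smoke-free days rises from 0.025 to as much as 0.05.

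The size of the gain is open to challenge as well. The z-test variance exceeds what a bounded proportion can have, and SAP 6.3.1 plans Poisson or negative binomial regression adjusted for baseline. Both points stand, so the gain is a range. It also depends on a CPD effect well above 2 to 3 cigarettes, although Holm never does worse than Bonferroni.

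Last, timing. The trial is open label, the synopsis ends enrolment on 9/30/2022, and the SAP was last modified on 11/21/2022. Relaxing a primary decision rule that late can look opportunistic. This is a reason to date the change and to make it only before comparative results are seen.

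**Conclusion.** The point holds as a missed efficiency and is optional. At the same family-wise two-sided 0.05, fixed 0.025 tests are uniformly less powerful than Holm, whatever the dependence between the endpoints. On the plan's z-test and effects, smoke-free-days power would rise from about .88 to .93 at N=400 and from .92 to .95 at N=450. With the variance capped for a bounded proportion, the gain on that scale is about 2 to 3 points. These figures rest on the 11-day difference, the 5.04% control rate, 20% attrition and a CPD difference of at least about 4 to 5 cigarettes. The ordering of the two methods rests on none of these.

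**What to change.** Make three edits before comparative results are seen:

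1. In SAP 6.1 and protocol 16.6.1, state that the two primary p-values are tested by Holm's procedure at family-wise two-sided 0.05.
2. In SAP 6.6 and protocol 16.6.6, state that alpha for the primary-endpoint subgroup tests stays at 0.025, so each sex or age subgroup is tested at 0.0125. Without this, the subgroup level would depend on the outcome of the Holm steps.
3. If 97.5% confidence intervals are reported, note that such an interval may include no effect when Holm rejects at a p-value between 0.025 and 0.05.

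The power sections (SAP 3.2.3, protocol 16.3) can keep their 0.025 figures if these are labelled as the level guaranteed to each endpoint. The cost is a few sentences and no new data or participants. In return, the team accepts the looser smoke-free-days error rate described above, and simultaneous intervals that match Holm are less simple than Bonferroni's.

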6.2. Describing the Study Population

Descriptive statistics will be performed for data collected at different visits. Daily Interactive Voice Response (IVR) data will be summarized by phase and by visit (according to the actual visit dates or scheduled visit dates if a visit is missed). Baseline data will be compared between the two studied conditions with t test or Wilcoxon rank sum test

for continuous variables and chi-square test or Fisher's exact test for categorical variables, which include sex, age, race, education, menthol status, dependence (FTND), CPD, nicotine metabolite ratio (NMR), and TNE. Baseline CPD and TNE are based on Phase 2.

6.3. Primary Endpoint Analysis

The primary endpoints are (1) the mean cigarettes (study and non-study cigarettes) smoked per day based on 7 days' Daily Interactive Voice Response (IVR)-Revised data before the week 12 visit; and (2) the number of smoke-free days out of the total number of days in Phase 3.

6.3.1. Primary Analysis

We expect the two groups to, on average, be balanced for important baseline characteristics due to randomization, so the primary analyses will be regressions for the difference in CPD and the number of smoke-free days between two conditions, adjusting for only the baseline value (the mean CPD and the percent of smoke-free days during Phase 2, respectively). Specifically, for the CPD outcome at week 12, we will use linear regression; for the number of smoke-free days, we will use Poisson regression or negative binomial regression when there is over-dispersion in the count data.

6.3.2. Secondary Analysis

For the Week 12 CPD and total number of smoke-free days, we will perform an adjusted analysis, adjusting for baseline value, study site (the randomization stratification factor), whether the Week 12 visit is pre-COVID or not, and any baseline characteristics (listed in Section 6.2) which are different at $p<0.20$, in multivariable regressions to improve efficiency.

For the CPD outcome measured repeatedly, we will use linear mixed effects models (Verbeke and Molenberghs, 2000). Fixed effects in the model will include: treatment group, visit, treatment group by visit interaction, baseline CPD, study site, whether the visit time is pre-COVID or not (as a time-dependent covariate), and any baseline characteristics (listed in Section 6.2) which are different at $p<0.20$. A random intercept for each subject will also be included in the model to account for within subject correlation.

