16.6.3. Primary Endpoint Analysis

The primary endpoints are (1) the mean cigarettes (study and non-study cigarettes) smoked per day based on 7 days' Daily Interactive Voice Response (IVR)-Revised data before the week 12 visit; and (2) the number of smoke-free days out of the total number of days in Phase 3.

Primary Analysis

We expect the two groups to, on average, be balanced for important baseline characteristics due to randomization, so the primary analyses will be regressions for the difference in CPD and the number of smoke-free days between two conditions, adjusting for only the baseline value (the mean CPD and the percent of smoke-free days during Phase 2, respectively). Specifically, for the CPD outcome at week 12, we will use linear regression; for the number of smoke-free days, we will use Poisson regression or negative binomial regression when there is over-dispersion in the count data.

Secondary Analysis

For the Week 12 CPD and total number of smoke-free days, we will perform an adjusted analysis, adjusting for baseline value, study site (the randomization stratification factor), whether the Week 12 visit is pre-COVID or not, and any baseline characteristics (listed in Section 16.6.2), which are different at $p<0.20$, in multivariable regressions to improve efficiency.

For the CPD outcome measured repeatedly, we will use linear mixed effects models.⁶¹ Fixed effects in the model will include: treatment group, visit, treatment group by visit interaction, baseline CPD, study site, whether the visit time is pre-COVID or not (as a time-dependent covariate), and any baseline characteristics (listed in Section 16.6.2) which are different at $p>0.20$. A random intercept for each subject will also be included in the model to account for within subject correlation.

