6.4. Secondary Endpoint Analysis

The secondary endpoints will first be summarized by treatment group using mean and standard deviation. We will use similar adjusted regression methods for the secondary endpoints as for the primary endpoints described in Section 6.3.2. Details are described as follows.

- For the percent change (relative to the measure at the end of Phase 2) of the biomarker measured repeatedly (weeks 4, 8, 12), we will use linear mixed effects models (Verbeke and Molenberghs, 2000). Fixed effects in the model will include: treatment group, visit, treatment group by visit interaction, study site, whether the visit time is pre-COVID or not (as a time-dependent covariate), and any baseline characteristics (listed in Section 6.2) which are different at $p<0.20$. A random intercept for each subject will also be included in the model to account for within subject correlation.
- For study cigarette smoked, similar analyses to total cigarettes per day will be performed.
- For the abstinence outcome, we will use logistic regression.

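### The adjusted models choose covariates by chance imbalance (p<0.20), so reported standard errors are somewhat too wide and most of the precision sought goes unreported

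*Combined protocol and SAP*

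**What the plan says.** SAP 6.2 provides for between-arm tests of baseline data: "Baseline data will be compared between the two studied conditions with t test or Wilcoxon rank sum test", with chi-square or Fisher's exact tests for categorical variables. The variables tested are those "which include sex, age, race, education, menthol status, dependence (FTND), CPD, nicotine metabolite ratio (NMR), and TNE", nine in all.

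SAP 6.3.1 fits the primary analysis of both primary endpoints "adjusting for only the baseline value". The tests in 6.2 play no part in it.

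SAP 6.3.2 then fits adjusted models for Week 12 CPD and for smoke-free days. They contain the baseline value, site, a pre-COVID indicator and "any baseline characteristics (listed in Section 6.2) which are different at $p<0.20$, in multivariable regressions to improve efficiency". The repeated-CPD mixed model has the same clause.

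SAP 6.4 carries this over: "We will use similar adjusted regression methods for the secondary endpoints as for the primary endpoints described in Section 6.3.2". The CEMA mixed model repeats the p<0.20 clause and lists no baseline-value covariate. SAP 6.5 uses the rule for days of non-combusted product use. Protocol 16.6.3 to 16.6.5 run in parallel. The protocol's mixed-model sentences in 16.6.3 and 16.6.4 print the inequality the other way round (p>0.20). That is a separate discrepancy to reconcile; this point takes the rule in the SAP's form.

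**The concern.** The stated purpose is efficiency. A covariate improves efficiency in proportion to how well it predicts the outcome, and the screen never looks at that. In a randomised trial a between-arm p-value for a baseline variable measures only chance. A strong predictor is therefore left out in about four trials out of five, and an irrelevant variable enters as often as a strong one.

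This also distorts the reported standard error. A predictor is left out exactly when it is well balanced, and so adds little to the actual error of the treatment estimate. Its variance still sits in the residual, so the model reports more uncertainty than there is.

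At stake are the adjusted analyses of both primary endpoints and the main analyses of the secondary endpoints. Two smaller matters follow. SAP 6.2 allows a choice between tests, so the same data could give different covariate sets. In the logistic model for abstinence, the conditional odds ratio being estimated depends on which covariates entered.

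**Working it through.** **Inputs.** From the SAP: nine candidates (6.2); threshold 0.20 (6.3.2); 1:1 allocation (3.1); N = 400 with 20% attrition (3.2), so 0.8 × 400 = 320 completers, 160 per arm; CPD SD 9.62 and control smoke-free rate 5.04% (Table 1); planned differences of 8 CPD (15 versus 7) and 11 of 84 days (3.2.3). Assumed, because the documents give no figure: R², the share of outcome variance that the candidates explain beyond the covariates always in the model, taken from 0 to 0.3.

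**The plan's own power figures.** For smoke-free days, r0 = .0504 and r1 = .0504 + 11/84 = .1814. Power = Φ[(r1 − r0)/√((r0 + r1)/n) − 2.2414]. With n = 160 per arm: .1310/√(.2318/160) = 3.44, and Φ(1.20) = .885 (stated .88). With n = 180: .920 (stated .92). CPD power exceeds .99 at both sizes, as stated. The SAP gives no figure for the efficiency of the adjusted models.

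**How many covariates enter.** Baseline CPD is always in the CPD models, which leaves 8 candidates: 8 × 0.20 = 1.6 expected, and 1 − 0.8⁸ = .83 for at least one (treating them as independent). For CEMA and abstinence all 9 are candidates: 1.8 expected, and 1 − 0.8⁹ = .87.

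**One covariate, closed form.** Let the covariate explain a share r, and let Z be its standardised imbalance, so that it is kept only if |Z| > 1.2816. Scale the unadjusted variance to 1.
- True variance under the rule: (1 − r) + r·E[Z²; |Z| < 1.2816] = (1 − r) + 0.35r = 1 − 0.65r.
- Average reported variance: 0.8 × 1 + 0.2 × (1 − r) = 1 − 0.2r.
- Reported SE over true SD: √[(1 − 0.2r)/(1 − 0.65r)] = 1.024, 1.050 and 1.081 at r = 0.1, 0.2 and 0.3.

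**Eight covariates, simulation.** Linear model, 320 completers, independent covariates, SD 9.62 before the candidates are added, 20,000 replicates per row. Power is for an illustrative 3-CPD difference. Its SE without extra covariates is 9.62 × √(2/160) = 1.076, so power is about Φ(3/1.076 − 1.96) = .80.

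| R² | Model | True SD | Mean reported SE | SE/SD | Size at .05 | Power |
|---|---|---|---|---|---|---|
| 0 | baseline only | 1.077 | 1.077 | 1.00 | .048 | .793 |
| 0 | p<0.20 rule | 1.087 | 1.085 | 1.00 | .049 | .787 |
| 0 | all 8 fixed | 1.091 | 1.090 | 1.00 | .050 | .784 |
| 0.1 | p<0.20 rule | 1.048 | 1.075 | 1.026 | .044 | .799 |
| 0.1 | all 8 fixed | 1.031 | 1.034 | 1.00 | .049 | .824 |
| 0.2 | p<0.20 rule | 1.017 | 1.063 | 1.046 | .041 | .815 |
| 0.2 | all 8 fixed | 0.975 | 0.975 | 1.00 | .050 | .867 |
| 0.3 | baseline only | 1.073 | 1.076 | 1.00 | .051 | .794 |
| 0.3 | p<0.20 rule | 0.972 | 1.052 | 1.084 | .035 | .833 |
| 0.3 | all 8 fixed | 0.908 | 0.912 | 1.01 | .050 | .909 |

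At nominal .025, the level for a primary endpoint, the rule's size is .024, .021, .019 and .015 at R² = 0, 0.1, 0.2 and 0.3. Other runs of similar design agreed closely; at R² = 0.1 power was .80 to .81 under the rule against .82 to .84 pre-specified.

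**Precision reported and precision achieved, R² = 0.3.** The reported SE falls from 1.076 to 1.052 under the rule (−2%), against 0.912 with the fixed list (−15%). The true SD falls from 1.073 to 0.972 (−9%), against 0.908 (−15%).

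**Count model.** A negative binomial check (2,000 replicates, four prognostic covariates) points the same way. SE/SD was 1.015 under the rule, against .972 baseline only and .971 fixed. True SD was .181 under the rule and .149 with the fixed list.

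**The case against.** The strongest reply is that little depends on this. The primary analysis does not use the rule, and planned CPD power exceeds .99. The candidates and the threshold are written down in advance. The rule also does no harm relative to baseline-only adjustment when the covariates predict: power .833 against .794 at R² = 0.3. By the closed form, the estimate keeps about 65% of the achievable variance reduction. All of that stands. What is mostly lost is the reported gain, and the comparison that matters is with a fixed list.

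A reader might infer that data-driven selection in an open-label trial inflates false positives or lets the analyst steer the result. The documents do not support that. Selection uses only arm and baseline data, never outcomes, and every linear-model size under the rule is at or below nominal. The choice between t and Wilcoxon, or chi-square and Fisher, leaves some latitude, but no effect of it has been shown.

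A fair objection is that R² is assumed. The documents give none, and at R² = 0 the effect vanishes. However, seeking efficiency by adjustment presupposes R² > 0. SAP 6.5 lists most of the same variables as predictors to explore, and SAP Table 1 shows control smoke-free rates of 2.85% at ages 25-44 against 8.04% at 45 and over.

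Two limits on scope also stand. Study CPD may receive the baseline-only model as well, since protocol 16.6.4 likens it to the primary endpoint analyses. The size and power figures come from linear models with independent covariates; the CEMA repeated-measures model was not simulated. A logistic check showed little inflation of the SE, so for abstinence the issue is mainly which odds ratio is estimated.

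**Conclusion.** The point holds as a modest one about non-primary models. For an assumed R² of 0.1 to 0.3 beyond the covariates always included, the rule makes the linear-model SE about 3% to 8% too wide and the size about .044 to .035 at nominal .05. Where power without extra covariates is about 80%, it forgoes roughly 2 to 8 percentage points of power against a fixed list. The direction is conservative throughout. It would be wrong to conclude that the rule creates false positives, undermines the primary analysis in SAP 6.3.1 or removes all benefit of adjustment. It falls well short of its own stated aim, chiefly in the main analyses of CEMA and 7-day abstinence and in the adjusted analyses of the primary endpoints.

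**What to change.** In SAP 6.3.2, 6.4 and 6.5, and protocol 16.6.3 to 16.6.5, replace the p<0.20 rule with a fixed covariate list drawn from the SAP 6.2 variables. Use either all of them or those expected to be prognostic, such as Phase 2 CPD, Phase 2 TNE, FTND, age and sex. Keep race and education for non-combusted product use, because protocol 2.3 reports both as predictors of it. Retain site and the COVID-period term as the SAP already defines it. For the logistic abstinence model, name a shorter fixed list if events are few; the SAP gives no expected rate of 7-day abstinence, so this needs a judgement in advance. Keep the between-arm tests in SAP 6.2, if at all, as description only.

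The cost is wording in both documents and a few degrees of freedom out of about 320. If the covariates turn out not to predict at all, the simulated power loss is under one percentage point (.784 with all eight fixed, against .787 under the rule and .793 with none).

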25.3. Record Retention

The investigator will retain study records including source data, copies of case report form, consent forms, HIPAA authorizations, and all study correspondence in a secured facility for at 7 years after the study file is closed with the IRB and FDA.

26. Subject Identifier

The subject identifier is an alpha-numeric combination. Example: E-B001 would be University of Minnesota's first subject.

Project Identifier: F= CENIC 2 Project 1

Site Identifier:

B = University of Minnesota

C = Brown University

E = University of Pennsylvania

F = Duke University

H = University of California – San Francisco

M = Wake Forest University

Subject ID:

B001-300

C001-300

E001-300

F001-300

H001-300

M001-300

Data Collection Time Point Identification Numbers:

94= Screening Visit

93=Baseline Visit 1

92=Baseline Visit 2

91=Marketplace Visit 1

00=Marketplace Visit 2 and Randomization

01= Week 1 visit

02= Week 2 visit

03= Week 3 visit (discontinued in conversion to telehealth visits)

04= Week 4 visit

06= Week 6 visit

08= Week 8 visit

10= Week 10 visit

12= Week 12 End of Intervention visit

16= 30 day follow-up visit

Additional visit (AV1, AV2, etc.)

86 = Termination Visit

27. Procedure Table	Platform	SCRN 94	BL 93	BL 92	MP 91	MP 00	Week 1-3 ³	Week 4	Week 6	Week 8	Week 10	Week 12	Follow -Up 16	Early Term
			Phase 1		Phase 2		Phase 3							
Phone Recruitment Questionnaire	REDCap	X												
VISIT ASSESSMENTS														
Weight (Height at screen)	Paper and REDCap	X	X	X	X	X	X	X	X	X	X	X	X	X
Pregnancy Test (if applicable)	Paper and REDCap			X		X		X		X		X		X
Heart Rate & BP	Paper and REDCap	X	X	X	X	X	X	X	X	X	X	X	X	X
Cotinine check, if needed	Paper and REDCap	X												
Breath Alcohol Test ⁴	Paper and REDCap	X	X	X	X	X	X	X	X	X	X	X	X	X
Urine Toxicology ⁴	Paper and REDCap	X											X	
Concomitant Medications	Paper and REDCap	X	X	X	X	X	X	X	X	X	X	X	X	X
Health Changes Questionnaire	Paper and REDCap			X	X	X	X	X	X	X	X	X	X	X
Adverse Events Assessment	Paper and REDCap			X	X	X	X	X	X	X	X	X	X	X
Product Accountability Log	Paper and REDCap				X	X	X	X	X	X	X	X		X
Procedures & Compliance Review	Paper				X	X	X	X	X	X	X	X	X	
End of Visit Evaluation	Paper and REDCap	X	X	X	X	X	X	X	X	X	X	X	X	X
SCREENING QUESTIONNAIRES														
Tobacco Use History and Exposure & Cessation Methods	Paper and REDCap	X												
Identifying Information	Paper and Access	X												
Demographics for Registration	Paper and REDCap						X							

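### The repeated-measures models for CPD, CEMA and several exploratory outcomes allow only a random intercept, so tests of how the effect changes over time can miss their nominal level by an amount the documents do not let us fix

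*Combined protocol and SAP*

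**What the plan says.** SAP 6.3.2 analyses repeated CPD with a linear mixed model whose fixed effects include "treatment group, visit, treatment group by visit interaction, baseline CPD, study site", a pre-COVID indicator and selected baseline covariates. Dependence within a participant is handled in one sentence: "A random intercept for each subject will also be included in the model to account for within subject correlation". SAP 6.4 repeats that sentence for CEMA: for the percent change "of the biomarker measured repeatedly (weeks 4, 8, 12), we will use linear mixed effects models". Protocol 16.6.3 and 16.6.4 say the same. SAP 6.5 sends the other biomarkers, perceived health risk and dependence back to these models.

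No residual covariance, random slope, robust standard error or degrees-of-freedom method is named. The SAP does not list the visits in the CPD model. The time-point list in protocol section 26 gives Phase 3 visits at weeks 1, 2, 3, 4, 6, 8, 10 and 12, with the entry "03= Week 3 visit (discontinued in conversion to telehealth visits" for week 3. That makes eight visits, or seven under telehealth.

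The primary CPD analysis is separate: "for the CPD outcome at week 12, we will use linear regression" (SAP 6.3.1).

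**The concern.** With independent residuals, a random intercept is compound symmetry. Weeks 1 and 12 are taken to be as correlated as weeks 1 and 2, and the spread at week 12 is taken to equal that at week 1. If correlation falls with time apart, the model understates the variance of a long-range change. If the spread changes, it uses the average variance at every visit, which is wrong for any one of them.

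This is the only model named for CEMA, a secondary endpoint. It is also the longitudinal analysis of a primary endpoint, and several exploratory outcomes inherit it. SAP 6.1 leaves no margin: "Analyses of the secondary and exploratory endpoints will not be adjusted for multiple comparisons". At stake are the error rates and confidence intervals for treatment-by-visit and visit-specific statements.

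**Working it through.** **Inputs from the documents.** At least 400 randomised 1:1 with 20% attrition (SAP 3.1, 3.2) gives 400 × 0.8 / 2 = 160 per arm, hence 2 × 160 − 2 = 318 degrees of freedom. CPD visits are the eight listed above (an assumption, since the SAP does not list them). CEMA visits are weeks 4, 8 and 12.

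**The plan's own figures.** It states no error rate for these models, only power. With "7 and 15 mean CPD for the VLNC and NNC group" and SD 9.62, the standardised CPD effect at 160 per arm is 8 / (9.62 × √(2/160)) = 7.44, so power exceeds .99, as stated. For smoke-free days, 11/84 = 0.131 over √((0.0504 + 0.1814)/160) = 0.0381 gives 3.44. Subtracting 2.24 gives power .885, against .88 stated. The sample-size inputs are therefore read correctly.

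**Assumed.** Correlation between weeks s and t is r^|s−t|, with r from 0.5 to 0.97. Data are complete unless stated, with no treatment effect.

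**Change contrasts.** In balanced data the fitted common correlation is the average, m, over all visit pairs. True variance over model variance is k = (1 − ρ(first, last)) / (1 − m), and the rejection rate is 2Φ(−1.96/√k).

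- CPD, r = 0.9: ρ(1,12) = 0.9^11 = 0.314 and m = 0.631 (28 pairs). k = 0.686/0.369 = 1.86, giving 15.1%.
- CEMA, r = 0.9: ρ(4,12) = 0.9^8 = 0.430 and m = (2 × 0.656 + 0.430)/3 = 0.581. k = 0.570/0.419 = 1.36, giving 9.3%.

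**Interaction test.** The statistic is distributed as Σλχ²(1) / [Σλχ²(318)/318], where λ are the eigenvalues of the centred true covariance. It is compared with the F(T−1, 318(T−1)) cut-off, T being the number of visits.

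| r per week | CPD interaction, 8 visits | CPD change, weeks 1-12 | CEMA interaction | CEMA change, weeks 4-12 |
|---|---|---|---|---|
| 0.5 | 6.3% | 6.7% | 5.0% | 5.5% |
| 0.7 | 8.0% | 9.3% | 5.1% | 6.7% |
| 0.8 | 9.0% | 11.6% | 5.2% | 7.8% |
| 0.9 | 10.2% | 15.1% | 5.5% | 9.3% |
| 0.95 | 10.9% | 17.2% | 5.7% | 10.1% |
| 0.97 | 11.1% | 18.1% | 5.8% | 10.4% |

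With seven CPD visits the interaction test rejects 5.9-10.0% for r from 0.5 to 0.95. Under true compound symmetry it rejects 5.0%. Adding a true random intercept to the decay changes nothing.

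**Independent visit-level noise.** If 25% of the non-intercept variance is independent from visit to visit, the CPD interaction falls to 5.7-7.0% and the week 1-12 contrast to 6.3-10.4%. At 50% noise they are 5.2-5.8% and 5.8-7.7%.

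**Changing SD.** At one visit, k is that visit's variance over the mean variance. For CEMA with SD 1, 1.2, 1.4: k = 1.96/1.467 = 1.34, or 9.0%. With SD 1, 0.85, 0.7: k = 0.49/0.7375 = 0.66, or 1.6%. For CPD, with SD linear in week, the figures are 9.8% and 1.4%. With constant SD, k = 1 and the contrast holds 5%.

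**Dropout.** Fitting the model by REML with 20% monotone dropout (1,200 trials per case, Monte Carlo error 0.5-1 point) gave 12.3% and 6.8% for the CPD interaction at r = 0.9 and 0.7. For CEMA it gave 6.4% and 3.5%.

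**Nominal 2.5%.** SAP 3.2.3 halves alpha for the primary outcomes: "The two-sided type-I error rate for each outcome (CPD and abstinence) was set at" 0.025. If that level were carried to repeated CPD, the interaction would reject 3.6-8.1% for r from 0.5 to 0.95.

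**After the change.** An unstructured covariance rejected 4.6-5.4% in every case run (r from 0.5 to 0.95; 3, 7 or 8 visits).

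**The case against.** A reader might infer that these tests run at about twice their nominal rate. The documents do not support that. They report no within-subject correlation and no variance by visit. Doubling of the interaction test at 5% needs seven or eight CPD visits, decay of about 0.9 or more per week and almost no independent noise. Self-report and assay error make some noise plausible, and 25% of it brings the CPD interaction down to 7.0% or less. For CEMA the interaction test is nearly exact throughout.

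A reader might also cite the protocol's rationale for 12 weeks (section 5.2.4) as evidence of decaying correlation. That passage expects early experimentation with other tobacco and nicotine products, then stabilisation on an uncertain time course. It concerns use of those products, and average change over time is what the visit and interaction terms model. It says nothing direct about the covariance of CPD or CEMA.

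The direction of a variance change is equally open: a falling SD makes the week-12 contrast conservative. Nor does the plan single out the interaction or any first-to-last contrast as a key test, and no stated hypothesis concerns the time course.

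All of this stands and limits the size of the point. It does not supply a reason for the constraint. The plan prescribes a specific covariance without support, and a neutral alternative is available at almost no cost.

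**Conclusion.** The point holds as a conditional one. A random intercept alone imposes equal variance and equal correlation. Where that is wrong, the CPD interaction test at nominal 5% runs at about 6-11% without visit noise and about 5-7% with 25-50% noise. Change contrasts run at about 6-18% for CPD and 5-10% for CEMA. Single-visit contrasts err in either direction, and only if the SD changes. The CEMA interaction test is little affected, at about 5-6%. The decay rates, noise shares and SD trends are assumptions.

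The trial's main conclusions are not in question: both primary endpoints use single-outcome regressions. The change is worth making because CEMA and repeated CPD rest on this model.

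**What to change.** In SAP 6.3.2 and 6.4, and for the 6.5 models that refer to them (protocol 16.6.3 to 16.6.5), replace the random-intercept sentence with wording such as:

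*Within-subject dependence will be modelled by an unstructured covariance across visits, with Kenward-Roger degrees of freedom. If the model does not converge, a random intercept will be combined with a spatial-power residual correlation in actual weeks and visit-specific variances; alternatively, robust (sandwich) standard errors will be used.*

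State which fallback comes first. Avoid Toeplitz or AR(1) structures indexed by visit order, because CPD visits are one week apart early on and two weeks apart later. List the visits in the CPD model and say how week 3 is handled.

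The cost is SAP wording and a small change to the model code. Covariance parameters rise from 2 to 8 × 9/2 = 36 for eight visits and to 3 × 4/2 = 6 for three, a small burden with 400 or more participants.
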